9.3.1.3 Supportive Analyses

There will be no supportive analysis for the primary efficacy endpoint.

9.3.1.4 Sensitivity Analyses

MMRM based on Multiple Imputation (MI)

An underlying assumption of the MMRM method is that data are missing at random. To minimize the amount of missing data, subjects who prematurely discontinue study drug treatment will continue to complete all scheduled study visits for spirometry and other efficacy assessments.

To assess the impact of missing data and the assumption that data are missing at random, a multiple imputation algorithm will be used if ≥10% of the subjects have missing change in ppFEV₁ at Week 24 in any treatment group. Missing absolute change from baseline in ppFEV₁ assessments will be imputed starting from the first visit with missing values, for which all subsequent visits through Week 24 are also missing. For intermediate missing data, i.e., missing values that fall between two non-missing ones, it is reasonable to assume that they are missing at

random and therefore will not be imputed. An MMRM analogous to that for the primary analysis of the primary endpoint will be applied to imputed datasets and the relevant MI estimators will be reported. Details for the MI steps are presented in [Appendix D](#).

9.3.1.5 Subgroup Analysis

Subgroup analyses of the primary efficacy endpoint will be performed using a model similar to that of the primary analysis for each of the following subgroups:

- Age at screening (<18, ≥18 years)
- Percent predicted FEV₁ at baseline (<70, ≥70)
- Sex (male, female)
- Geographic region (North America, Europe [including Australia])
- Prior use of inhaled antibiotic (Yes, No)
- Prior use of dornase alfa (Yes, No)
- Prior use of inhaled bronchodilator (Yes, No)
- Prior use of inhaled hypertonic saline (Yes, No)
- Prior use of inhaled corticosteroids (Yes, No)
- Prior use of azithromycin (Yes, No)
- Infection with *Pseudomonas aeruginosa* within 2 years prior to screening (Positive, Negative)

The MMRM used for the primary analysis will be used for the subgroup analysis, where the same model will be applied to each category of the subgroup. Note that for the subgroup analysis based on age and sex, the covariate of age at screening (<18 versus ≥18 years of age) and sex (male versus female) from the MMRM will be removed, respectively. The adjusted means with 2-sided 95% confidence intervals will be provided. Furthermore, the estimated treatment difference at Week 4 in different categories within a subgroup will also be presented in a forest plot. Note: The results from the subgroup analysis should be interpreted with caution in the cases where sample sizes are small.

9.3.2 Analysis of Key Secondary Variables

9.3.2.1 Definition of Variables

Pulmonary exacerbation (PEX): A PEX is defined as a new event or change in antibiotic therapy (IV, inhaled, or oral) for any 4 or more of the following signs/symptoms:

- Change in sputum
- New or increased hemoptysis
- Increased cough
- Increased dyspnea
- Malaise, fatigue, or lethargy

- Temperature above 38°C (equivalent to approximately 100.4°F)
- Anorexia or weight loss
- Sinus pain or tenderness
- Change in sinus discharge
- Change in physical examination (PE) of the chest
- Decrease in pulmonary function by 10%
- Radiographic changes indicative of pulmonary infection

The **PEx analysis period** will include the time from the first dose date of study drug until the last efficacy assessment, which may be collected up to the Week 24 Visit or the earlier of Day 169 and the end of study participation if subject does not have the Week 24 Visit.

The number of PEx through Week 24 is then defined as the total number of PEx for each treatment group during the PEx analysis period.

Sweat chloride (SwCl): the SwCl value for a given visit will be calculated as the mean of the non-missing sweat chloride measurements obtained on the left and right arms at that visit. If one of the two arm measurements at a time point is missing, the other will be used as the mean. A volume ≥ 15 μL is required for an accurate determination of sweat chloride. Any results reported as having volume < 15 μL will be considered missing. Any sweat chloride values reported as < 10 mmol/L or > 160 mmol/L will be considered missing.

Cystic Fibrosis Questionnaire-Revised (CFQ-R): The CFQ-R^{1,4,6} is a validated CF-specific instrument that measures quality-of-life domains. This study utilizes three different versions of CFQ-R:

- CFQ-R for Children ages 12 and 13
- CFQ-R for Adolescents and Adults (subjects 14 years and older)
- CFQ-R for Parents/Caregivers (subjects 13 years and younger)

In all three versions, specific question belonging to a domain is scored 1, 2, 3, or 4. The CFQ-R domain score, e.g., physical domain score or respiratory domain score, is defined as a scaled score as follows:

Scaled score for a domain = $100 \times (\text{mean (scores of all questions in the domain)} - 1)/3$, where the score from a negatively phrased question is first reversed, i.e., reversed score = $5 - \text{actual score}$, so that 1 always represents the worst condition and 4 the best condition. The (scaled) domain score ranges from 0 (worst condition) to 100 (best condition). The scaled score for a specific domain will not be calculated if more than half of the questions in the domain have missing scores.

The (scaled) domain score from the CFQ-R for Children ages 12 and 13 and for Adolescent and Adults will be pooled for the analysis purpose.

Body mass index (BMI): the BMI at each visit is calculated using the weight and height at each visit as follows:

$$\text{BMI} = \frac{\text{Weight (kg)}}{\text{Height (m}^2\text{)}}$$

9.3.2.2 Analysis Method

Absolute change in ppFEV₁ through Week 24: Analysis of this variable will be based on an MMRM that is exactly the same as the primary efficacy variable. However, the Day 15 Visit will not be included in the estimation of the average treatment effect through Week 24 as the treatment effect is not expected to reach the steady state at Day 15.

Number of PEx through Week 24: Analysis of this variable will be performed using a negative binomial regression model with a fixed effect for treatment, as well as continuous baseline ppFEV₁, age at screening (<18 versus ≥18 years of age), and sex (male versus female) as covariates. The logarithm of the subject-specific PEx analysis period duration (in years) will be treated as the offset in the model.

Absolute change in SwCl from baseline through Week 24: Analysis of this PD variable will be based on an MMRM similar to the analysis of the primary efficacy variable. Data obtained from Week 4, Week 8, Week 12, and Week 24 Visits will be included in the model and all of these visits will be included in the estimation of the average treatment effect through Week 24.

Absolute change in the CFQ-R respiratory domain score from baseline through Week 24: Analysis of this domain will be based on an MMRM similar to the analysis of the primary efficacy variable. Data obtained from Week 4, Week 8, Week 12, Week 16, and Week 24 Visits will be included in the model and all of these visits will be included in the estimation of the average treatment effect through Week 24.

Absolute change in BMI from baseline at Week 24: Analysis of this variable will be based on an MMRM similar to the analysis of the primary efficacy variable. Data obtained from Day 15, Week 4, Week 8, Week 12, Week 16, and Week 24 Visits will be included in the model.

Absolute change in SwCl from baseline at Week 4: Analysis of this PD variable will be based on an MMRM similar to the analysis of the primary efficacy variable. Data obtained from Week 4, Week 8, Week 12, and Week 24 Visits will be included in the model to estimate the treatment effect at Week 4.

Absolute change in CFQ-R respiratory domain score from baseline at Week 4: Analysis of this domain will be based on an MMRM similar to the analysis of the primary efficacy variable. Data obtained from Week 4, Week 8, Week 12, Week 16 and Week 24 Visits will be included in the model to estimate the treatment effect at Week 4.

To assess the longitudinal profile of the efficacy and pharmacodynamic assessments with repeated measures up to Week 24, the LS mean (SE) of the within-treatment group change from baseline at each post-baseline visit along with the 95% CI will be estimated from the corresponding MMRM. The LS mean (SE) of the treatment difference between VX-445/TEZ/IVA and triple placebo at each post-baseline visit will be provided along with the corresponding 95% CI and *P* value. The LS mean (SE) at each visit will also be plotted by treatment group. In addition, the post-baseline raw values and the absolute change from baseline at each post-baseline visit will be summarized descriptively (n, mean, SD, median, minimum, and maximum).

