Another key secondary endpoint is the number of PEx through Week 24. Assuming a rate of PEx for the placebo group of 0.6 over 24 weeks and a 10% dropout rate, with 180 subjects and the overdispersion parameter of 0.5 in each treatment group, the power to detect a 40% reduction in the PEx rate for TC group compared to placebo group is approximately 80%, based on a 2-sided, 2-sample negative binomial regression model test for the ratio of rates, at a significance level of 0.05.

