7.2 Sample Size and Power

Approximately 360 subjects will be enrolled and randomized (1:1) to the VX-445/TEZ/IVA arm or the triple placebo arm. This sample size was determined to provide adequate power for the key secondary endpoint of the number of PEX through Week 24. Information regarding the powering of primary and selected key secondary endpoints is provided below. [REDACTED]

Power for Primary Efficacy Endpoint

The primary efficacy endpoint is the absolute change in ppFEV₁ from baseline at Week 4. The primary null hypothesis to be tested is that the mean absolute change in ppFEV₁ from baseline at Week 4 is the same for the 2 treatment groups, VX-445/TEZ/IVA and placebo. If the number of subjects included in the IA is 140, the null hypothesis will be tested at a 2-sided significance level of 0.044 during the IA and at an overall 2-sided significance level of 0.05. See Section 7.5 for details on the significance level for hypothesis testing during the IA.

Assuming a within-group SD of 7 percentage points and a 5% dropout rate at Week 4, an IA sample size of 70 subjects in each treatment group will have approximately 98% power to detect a difference between the treatment groups of 5.0 percentage points for the mean absolute change in ppFEV₁ from baseline at Week 4, based on a 2-sided, 2-sample *t*-test at a significance level of 0.044. If the *P* value fails to cross the efficacy boundary during the IA (*P* value ≥ 0.044 ; assuming 140 subjects included in the IA), the primary endpoint of absolute change in ppFEV₁ from baseline at Week 4 will be tested after all subjects complete study participation at an alpha of 0.01. Assuming a 10% dropout rate at Week 24, a final analysis sample size of 180 subjects in each treatment group will have approximately 99% power to detect a difference between the treatment groups of 5.0 percentage points for the mean absolute change in ppFEV₁ from baseline at Week 4, based on a 2-sided, 2-sample *t*-test at a significance level of 0.01.

Power for Selected Secondary Endpoints

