A key secondary endpoint is the absolute change in ppFEV₁ from baseline through Week 24. Assuming a within-group SD of 7 percentage points and a 10% dropout rate at Week 24, a sample size of 180 subjects in each treatment group will have approximately 99% power to detect a difference between the treatment groups of 5.0 percentage points for the absolute change in ppFEV₁ from baseline through Week 24, based on a 2-sided, 2-sample *t*-test at a significance level of 0.05.

A key secondary endpoint is the number of PEx through Week 24. Assuming a rate of PEx for the placebo group of 0.6 over 24 weeks and a 10% dropout rate, with 180 subjects and the overdispersion parameter of 0.5 in each treatment group, the power to detect a 40% reduction in the PEx rate for VX-445/TEZ/IVA group compared to placebo group is approximately 80%, based on a 2-sided, 2-sample negative binomial regression model test for the ratio of rates, at a significance level of 0.05.

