7.3 Randomization

Subjects will be randomized (1:1) to the VX-445/TEZ/IVA arm or to the triple placebo arm. Randomization will be stratified by ppFEV₁ determined during the Screening Period (<70 versus ≥ 70), age at the Screening Visit (<18 versus ≥ 18 years of age), and sex (male versus female).

An interactive web response system (IWRS) will be used to assign subjects to treatment. The randomization code list will be produced by Vertex Biometrics or a qualified randomization vendor.

Randomization will occur before the first dose of study drug during the Treatment Period and may occur on either Day 1 or Day -1.

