9.2.3 Medical History

Medical history will be coded by using the Medical Dictionary for Regulatory Activities (MedDRA). For the FAS, medical history will be summarized descriptively by system organ class (SOC) and preferred term (PT). The corresponding data listing will also be provided.

In addition, the number of subjects reported to have had positive cultures for respiratory pathogens within the 2 years prior to screening (i.e., answered yes on the respiratory microbiology form) will be summarized for the FAS. The corresponding data listing will be provided. Hospitalization and clinic visit history in the year prior to the signing of informed consent will be listed.

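### The PEx count model is valid at its stated 80% power, but it forgoes a modest gain by leaving out prior-year hospitalization history that is available and only listed

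*SAP*

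**What the plan says.** **Model.** For the number of PEx through Week 24, SAP 9.3.2.2 states: "Analysis of this variable will be performed using a negative binomial regression model with a fixed effect for treatment". The covariates are continuous baseline ppFEV1, age group and sex, and the offset is the log of each subject's PEx analysis period. Protocol 12.3.3.1.2 names the same covariates, and also for the Cox model of time to first PEx. Addendum 2 to the SAP (5.2.1) adds a Poisson fallback if the negative binomial fit does not converge, without changing the covariates.

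**History.** SAP 9.2.3 states: "Hospitalization and clinic visit history in the year prior to the signing of informed consent will be listed". The history is not a covariate, not a stratification factor (SAP 7.3) and not a subgroup factor for the primary endpoint (SAP 9.3.1.5).

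**Sizing.** SAP 7.2 says of the 360 subjects: "This sample size was determined to provide adequate power for the key secondary endpoint", meaning the number of PEx. The calculation there starts from "Assuming a rate of PEx for the placebo group of 0.6 over 24 weeks and a 10% dropout rate"; each arm is given 180 subjects and a dispersion of 0.5. Protocol 12.1 concludes that "the power to detect a 40% reduction in the PEx rate for TC group compared to placebo group is approximately 80" percent.

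**Hierarchy.** In SAP 9.3.2.3, PEx is second of seven key secondary endpoints tested in fixed order.

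**The concern.** A subject's own recent history is a natural candidate for explaining who exacerbates, and the plan carries unexplained between-subject variation as a dispersion of 0.5. The documents themselves connect the two: the schedule of assessments groups PEx with CF hospitalizations as outcome-related events, and SAP 9.3.4.3 analyses PEx that require hospitalization. Leaving an available baseline variable out of the model gives up whatever precision it would bring.

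This matters more here than for the other endpoints. PEx has about 80% planned power, against 98-99% for the ppFEV1 tests. If it misses, the five tests behind it cannot be claimed formally: SwCl and CFQ-R through Week 24, BMI at Week 24, and SwCl and CFQ-R at Week 4.

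**Working it through.** **Inputs from SAP 7.2:** 180 per arm, 10% dropout, placebo rate 0.6 over 24 weeks, 40% reduction, dispersion k = 0.5, two-sided alpha 0.05. So n = 180 × 0.9 = 162 per arm, and the active rate is 0.6 × 0.6 = 0.36.

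**1. Reproduce the stated power.** For a Wald test on the log rate ratio:

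- Var = (1/0.6 + 1/0.36 + 2k)/n = (1.667 + 2.778 + 1.0)/162 = 0.0336, so SE = 0.1833
- |ln 0.6|/SE = 0.5108/0.1833 = 2.787
- Power = Φ(2.787 − 1.960) = 79.6%

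A pooled-rate null variance gives 81.0%. The plan's figure of about 80% is correct.

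**2. Ceiling.** If covariates explained all overdispersion (k = 0), then Var = 4.444/162 and power = 87.0%. No covariate could bring this design to 90%.

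**3. Add a binary history covariate.** Its prevalence p and PEx rate ratio R are not in the documents, so both are assumed over a range. Marginal dispersion is held at 0.5:

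- c = 1/(1 − p + pR), which keeps the mean rate unchanged
- explained part v = p(1 − p)(R − 1)²c²
- residual dispersion k' = 1.5/(1 + v) − 1
- information per subject at mean μ: I(μ) = Σ w·μx/(1 + k'μx), over (w, x) = (1 − p, c) and (p, cR)
- Var = [1/I(0.6) + 1/I(0.36)]/162

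Worked case, p = 0.3 and R = 2: c = 0.769, v = 0.124, k' = 0.334, I(0.6) = 0.4915, I(0.36) = 0.3176. Var = (2.034 + 3.148)/162 = 0.0320, SE = 0.1789, and power = Φ(2.856 − 1.960) = 81.5%.

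Across p = 20%, 30%, 40% and 50%:

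| Rate ratio R | Residual k' | Power | Gain over 79.6% (points) |
|---|---|---|---|
| 1.25 | 0.48-0.49 | 79.7-79.8% | about 0.2 |
| 1.5 | 0.44-0.45 | 80.1-80.2% | 0.5-0.7 |
| 2 | 0.33-0.35 | 81.3-81.5% | 1.7-1.9 |
| 2.5 | 0.23-0.27 | 82.3-83.0% | 2.8-3.4 |
| 3 | 0.13-0.20 | 83.3-84.5% | 3.7-4.9 |

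In subjects, the worked case has a variance ratio of 5.444/5.183 = 1.050, equivalent to about 18 more randomized on 360. At p = 0.3 the corresponding figures for R = 1.5 and R = 3 are about 6 and 50.

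**4. Simulation check** (1,500 trials each; standard error √(0.8 × 0.2/1500), about 1 point). Unadjusted versus adjusted power was 81.5% versus 81.8% (p = 0.3, R = 1.5), 81.4% versus 82.8% (p = 0.3, R = 2) and 80.2% versus 84.1% (p = 0.4, R = 3). Between 1% and 9% of adjusted fits did not converge and were dropped, so the adjusted figures are approximate.

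**5. Cost of missing history.** SAP 9.1 leaves missing data unimputed by default, so a subject without history would fall out of the regression. Missingness is assumed, at p = 0.3:

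- 2.5% missing (158 per arm), R = 1.5: 79.2%
- 5% missing (154 per arm), R = 2: 79.5%
- 5% missing, history not prognostic: 77.5%

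Without a missing-history rule, a few percent of missing forms would cancel the gain.

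**The case against.** The case for leaving the model alone is that nothing in it is wrong. The test is valid under randomization, the protocol and SAP agree, and the power is correctly stated. All of that stands.

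It is also fair that the size of the gain rests on unknown inputs:

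- **The history is a proxy.** SAP 9.2.3 does not say that the admissions are pulmonary or CF-related. A PEx by definition needs new or changed antibiotics by any route with at least four signs or symptoms, and no admission.
- **The top of the range is demanding.** At 30% prevalence and a rate ratio of 3, one yes/no item would remove about 74% of the overdispersion (0.5 to 0.13).
- **Overlap is ignored.** The calculation credits the whole effect to hospitalization, although ppFEV1, age and sex may already carry part of it. The plan does not say whether 0.5 is net of those covariates.

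Two procedural costs also stand. The protocol fixes the covariates, so SAP wording alone is not enough. And a smaller residual dispersion makes a failed negative binomial fit, and hence the Poisson fallback, somewhat more likely.

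These points limit the claim but do not remove it. A missing-history rule deals with the loss of subjects, and the rest of the cost is small.

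A reader might infer that the PEx analysis is biased or underpowered, that hospitalization history is known to be the best available predictor, or that adding it can only help. The documents support none of these: the planned power reproduces, no prognostic data are given, and step 5 shows how the addition could lose power.

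**Conclusion.** This is a missed efficiency, not an error. The planned PEx test is sound and its 80% power is right. Adding prior-year hospitalization would raise power by about 0.2 to 5 points for rate ratios from 1.25 to 3, and by about 0.5 to 2 points for ratios of 1.5 to 2. The ceiling is about 87%.

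These figures assume 20-50% prevalence, total dispersion 0.5, 162 evaluable per arm, no missing history and no overlap with the existing covariates; overlap would lower them. The change is worth making because it is cheap and falls on the weakest planned link in the hierarchy, not because the gain is large.

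One limit: Addendum 2 cites a SAP Version 1.1 EUR and an Addendum 1 that cannot be identified in the supplied text, so a change there cannot be excluded.

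**What to change.** Before unblinding, and through the blinded study team, issue a SAP amendment or addendum, recorded as a modification of the model specified in protocol 12.3.3.1.2. Addendum 2 already revisits this analysis by the same route. It should:

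- add prior-year hospitalization (0 versus at least 1) as a covariate to the PEx negative binomial model (SAP 9.3.2.2), its Poisson fallback (Addendum 2, 5.2.1) and the time-to-first-PEx Cox model (SAP 9.3.3.2);
- state that subjects with missing history stay in the analysis, for example in a missing or none-reported category;
- keep the present model as a supportive analysis.

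First confirm, on blinded data, that the history form supports this coding and is reasonably complete. If it does not, record that as the reason for leaving the model unchanged.

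Cost: one extra model term, a documented change to a confirmatory model, and a slightly higher chance of triggering the Poisson fallback if residual dispersion becomes small. On the face of SAP 9.2.3, no new data and no extra subjects are needed.

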9.3.2.3 Multiplicity Adjustment

The Lan and DeMets³ alpha spending function will be applied to the primary endpoint of the absolute change in ppFEV₁ at Week 4 to control the overall type I error rate of 0.05 such that an alpha of 0.01 will be preserved for the final analysis.

If the number of subjects included in the IA is 140, the primary endpoint of the absolute change from baseline in ppFEV₁ at Week 4 will be tested at an alpha of 0.044 during the IA. The actual alpha at the IA (α_0) will be determined based on the actual number of subjects included in the interim Full Analysis Set. If the study does not cross the efficacy boundary during the IA (P value $\geq \alpha_0$), then the primary endpoint will be tested at an alpha of 0.01 at the final analysis when all subjects complete the study participation. See Section 7.5 for more details.

The key secondary endpoints will be formally tested at an alpha of 0.05 at the final analysis when all subjects complete study participation only if the primary endpoint is statistically significant at the IA or at the final analysis. A hierarchical testing procedure will be used to control the type I error rate for the multiple key secondary endpoints tested at an alpha of 0.05. For a test at any step to be considered statistically significant within the testing hierarchy, it must be statistically significant, and all previous tests (if any) within the hierarchy must be statistically significant at the 0.05 level. The testing order of the key secondary endpoints is as follows:

- Absolute change in ppFEV₁ from baseline through Week 24
- Number of PEx through Week 24
- Absolute change in SwCl from baseline through Week 24
- Absolute change in CFQ-R respiratory domain from baseline through Week 24
- Absolute change in BMI from baseline at Week 24
- Absolute change in SwCl from baseline at Week 4
- Absolute change in CFQ-R respiratory domain score from baseline at Week 4

